5.2.4 Pacritinib Dosage Management Guidelines for Diarrhea

The need for managing GI effects of pacritinib, particularly diarrhea, should be anticipated. A careful baseline evaluation of bowel habits (frequency and consistency of bowel movements) should be obtained at baseline for all patients. At the baseline visit, all patients in the pacritinib arm will be provided with a prescription (and instructions to fill that prescription) for loperamide (Imodium®) or a similarly effective antidiarrheal drug. Patients will be instructed to start taking the prescribed loperamide or other antidiarrheal drugs per package and physician instructions as soon as they notice any changes in frequency or consistency of bowel movements after starting study treatment. Early intervention for diarrhea should be initiated for patients in the pacritinib arm with increases of one grade or more in diarrhea (Appendix 7). At the investigator's discretion, prophylactic use of antidiarrheals may be initiated for patients or populations in whom it is judged necessary to enhance patient safety. Standard supportive care measures to control symptoms of GI toxicity such as diarrhea, constipation, and nausea should be provided.

Treatment with antidiarrheals is advised for all patients who experience new-onset diarrhea (Table 4). Dose modifications for patients with diarrhea, nausea, and vomiting that is considered at least possibly related to study drug are described in Table 4.

Table 4. Treatment Toxicity and Dosage Management for drug-related Diarrhea, Nausea, Vomiting

CTCAE v5 Toxicity Grade	Management/Action
1	No Change
2	
Hold pacritinib for up to seven daysIf the toxicity resolves to grade ≤ 1 or the baseline grade within seven days, treatment will be resumed at the same levelIf the toxicity recurs after the restart at the same dosage level, treatment may only be resumed at the next lower dosage level start at 50% of the dose once resolved (100 mg BID)
3	
Hold treatment.If the toxicity resolves to grade ≤ 1 or the baseline grade within seven days, treatment may be resumed at the same level or the next lower dosage. Concomitant antidiarrheal treatment is required for patients restarting pacritinib at the 100 mg QD dosage level.If the toxicity recurs after the restart at the same dosage level, treatment may only be resumed at the next lower dosage level.If the toxicity resolves to grade ≤ 1 or the baseline grade after more than seven days, treatment may be resumed only at the next lower dosage level. Discontinuation is required if on hold from the 100 mg QD dosage level. Concomitant antidiarrheal treatment is required for patients restarting pacritinib at the 100 mg QD dosage level.

CTCAE v5 Toxicity Grade	Management/Action
	
 If the toxicity recurs after the restart at the lower dosage level, pacritinib treatment must be discontinued.
4	
 Discontinue pacritinib

5.2.5 Pacritinib Dosage Management Guidelines for Pacritinib-Related Nonhematologic Toxicities Other than QTc Prolongation, Decreased Cardiac Ejection Fraction, Other Cardiac Toxicities or Diarrhea

As defined in Table 5, a maximum of two dosage reductions are allowed for pacritinib-related nonhematologic toxicities other than QTc prolongation, decreased cardiac ejection fraction, or diarrhea.

Table 5. Treatment Toxicity and Dosage Management: Pacritinib-Related Nonhematologic Toxicities Other than QTc Prolongation, Decreased Cardiac Ejection Fraction, Other Cardiac Toxicities or nausea, vomiting and Diarrhea

CTCAE v5 Toxicity Grade	Management/Action
1 or 2	No change.
3	
 Hold treatment. If the toxicity resolves to grade ≤ 1 or to the baseline grade within seven days, treatment may be resumed at the same level or the next lower dosage, at the discretion of the investigator after discussion with the Sponsor. Toxicity that does not resolve to grade <1 or to the baseline grade within seven days requires dosage reduction to the next lower dosage.
4	
 Hold treatment. If the toxicity resolves to grade <1 or to the baseline grade within seven days, treatment may be resumed, but the dosage will be reduced by one dosage from the level at which the toxicity was observed. If grade 4 toxicity occurs at the lowest dosage of 100 mg QD, the patient should be discontinued from the study.

5.3 Concomitant and Excluded Therapies

Patients should receive full supportive care, including transfusions of blood and blood products, antidiarrheal and antiemetic agents, and antibiotics when appropriate.

Patients may not receive other investigational agents during the study.

Patients must not receive treatment with any potent CYP3A4 inhibitors for one week prior to the administration of pacritinib and during treatment with pacritinib.

The following therapies and procedures are prohibited for all patients during the washout period and throughout the treatment phase of the study.:

- Strong CYP3A4 inhibitors (Appendix 3) and strong CYP450 inducers (Appendix 4), except as needed to treat AEs, with Medical Monitor approval.
- Any drugs with significant potential for QTc prolongation (Appendix 6), except as needed to treat AEs, with PI approval.

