Pacritinib exposure and the occurrence of the most common AEs of interest (diarrhea, vomiting, nausea, thrombocytopenia, hemorrhage, anemia, and cardiovascular events) were evaluated using clinical data from PERSIST-1, PERSIST-2, and the interim data from PAC203. The exposure-safety analysis showed no correlation between pacritinib exposure and the occurrence of the most common AEs of interest except for GI AEs (including diarrhea, vomiting, and nausea) and cardiovascular (CV) AEs. The model predicted the probability of GI AEs for the 200-mg BID dose was approximately 14% and approximately 7% for CV AEs.

Taken together, the exposure-efficacy and exposure-safety analyses based on the PERSIST studies and the safety and efficacy observations from the PAC203 Phase 2 study indicate that the 200 mg BID is an appropriate dose for investigation in a phase 3 study.

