5.1.2 Dosage, Route, and Mode of Administration

Patients assigned to pacritinib will be supplied with 100-mg capsules of pacritinib. Patients will take two 100-mg capsules of pacritinib BID, orally, at the same time of day, with or without food. On days when ECGs are to be obtained, pacritinib will be administered in the clinic to facilitate the performance of predose assessments. Any missed or vomited doses should not be retaken or replaced.

Regimen Description				
Study agent	Route	Premedication; precautions	Dose	Duration
Pacritinib	Oral	None	200 mg b.i.d	Continue treatment until progression of disease (at least 12 weeks) or meeting discontinuation criteria.

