5.4 Dietary Restrictions

None.

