7.6 Contraindications

Supportive care therapies, except when prohibited by any of the below provisions, are permitted, including the use of low-dose aspirin. Corticosteroids (up to 20 mg/day of prednisone or equivalent) and/or hydroxyurea may be used for up to two weeks during the first month of treatment with pacritinib.

The following therapies and procedures are prohibited throughout the study:

- Antiplatelet or anticoagulation agents, with the exception of \leq 100 mg/day of aspirin.
- Growth factor therapies, including erythropoietin and thrombopoietin.
- Strong CYP3A4 inhibitors and strong CYP450 inducers, except as needed to treat AEs, with study PI approval.
- Any drugs with significant potential for QTc prolongation (Appendix 6), except as needed to treat AEs, with medical monitor approval.
- Splenic irradiation or splenectomy.

Ongoing Hemorrhage: Patients with active bleeding should not begin or continue treatment with pacritinib. Reports of serious bleeding events, including life-threatening and fatal events, have been reported in association with pacritinib use. Pacritinib should be discontinued before planned surgery.

Hypersensitivity: Patients with a known hypersensitivity to the active ingredient or any of the excipients of the drug product should not take pacritinib.

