APPENDIX 3. SELECTED STRONG INHIBITORS OF CYP3A4

Boceprevir	ciprofloxacin	clarithromycin
Conivaptan	erythromycin	fluconazole
Grapefruit	grapefruit juice	indinavir
Itraconazole	ketoconazole	lopinavir
Mibepradil	nefazodone	nelfinavir
Norfloxacin	posaconazole	Quinidine
Ritonavir	saquinavir	Seville oranges
star fruit	telaprevir	telithromycin
troloandomycin	voriconazole	

This list is not comprehensive. When considering using an agent that could be a potential CYP3A4 inhibitor, please discuss this with the pharmacy team.

Source: <http://medicine.iupui.edu/clinpharm/ddis/table.asp> and
<http://www.pharmacytimes.com/issue/pharmacy/2008/2008-09/2008-09-8687>.

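### Section 5.4 sets no dietary restrictions, while Section 5.3 bans the strong CYP3A4 inhibitors of Appendix 3, four of whose entries are foods

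*Combined protocol and SAP*

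**What the plan says.** Section 5.3 deals with CYP3A4 inhibition twice. One sentence reads: "Patients must not receive treatment with any potent CYP3A4 inhibitors for one week prior to the administration of pacritinib and during treatment with pacritinib". The list of prohibitions that follows, which applies to every patient in washout and on treatment, includes "Strong CYP3A4 inhibitors (Appendix 3) and strong CYP450 inducers (Appendix 4), except as needed to treat AEs, with Medical Monitor approval".

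Appendix 3 is titled as a selection of strong CYP3A4 inhibitors. Most of its entries are drugs, but it also contains grapefruit, "grapefruit juice", "Seville oranges" and star fruit.

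Section "5.4 Dietary Restrictions" follows directly after 5.3, and its whole content is the word None. It does not refer to Appendix 3.

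Three other places bear on the reading:

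- Section 5.1.2 tells patients to take the capsules "at the same time of day, with or without food".
- Exclusion criterion 7 (Eligibility Confirmation) bars prohibited medications in the seven days before Cycle 1 Day 1 and points to Appendices 3 and 4 as the list.
- Exclusion criterion 8 bars systemic treatment with a strong CYP3A4 inhibitor in the 14 days before Day 1, and also cites Appendix 3.

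**The concern.** A coordinator who is asked whether a patient may drink grapefruit juice would look under the heading on diet and find that nothing is restricted. The same question taken to Section 5.3 and its appendix gets the opposite answer. Site staff cannot follow both.

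What is at stake is drug exposure and tolerability. Section 1.5.5 reports no correlation between pacritinib exposure and the common adverse events of interest "except for GI AEs (including diarrhea, vomiting, and nausea) and cardiovascular (CV) AEs". Those are the events that would matter if exposure rose unintentionally, and the dose-management tables attach holds, reductions or discontinuation to them. The protocol takes strong CYP3A4 inhibition seriously enough to prohibit it during treatment and to exclude men recently treated with such drugs, so its diet section should not point the other way.

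**Working it through.** There is no statistical figure to reproduce. The check is a count and a comparison of texts.

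**Count.** Appendix 3 is laid out as eight rows of three entries and one row of two: 8 × 3 + 2 = 26. Food or drink entries: grapefruit, grapefruit juice, Seville oranges, star fruit = 4 of 26. These are three distinct fruits, one of them also listed as juice.

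**Where Appendix 3 is used.** The text cites it in three places: exclusion criterion 7, exclusion criterion 8 and Section 5.3.

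**Reading A: the list defines the ban.** Section 5.3 identifies the prohibited inhibitors by reference to Appendix 3, and its only exception is treatment of adverse events. The four foods are on the list, so they are prohibited in washout and on treatment. Section 5.4 is then wrong. Exclusion criterion 7 cites the same list, so a man who ate one of these foods in the seven days before Cycle 1 Day 1 could arguably be ineligible.

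**Reading B: the ban covers medicines only.** Section 5.4 is then correct. Exclusion 7 speaks of medications, exclusion 8 of systemic treatment, and Section 5.3 of therapies and procedures. None of the three uses of Appendix 3 reaches the foods, so the four entries do nothing anywhere in the protocol.

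**Could None refer only to meal timing?** Section 5.1.2 already covers meal timing, and Section 1.5.3 gives the basis for it (no food effect on absorption). The heading of 5.4 is about diet in general. A meal-timing statement says nothing about particular foods that inhibit the enzyme.

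**Is it resolved elsewhere?** No other section in the text exempts the foods or gives a dietary instruction. Section 7.5 describes a diary for capsules taken and side effects, and the study calendar records concomitant medications. Neither mentions diet. The diary file and the consent form are not in the text available for this review.

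Under A, Section 5.4 must change. Under B, Appendix 3 must change. No reading leaves all three texts in order.

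**The case against.** The strongest reply is that reading B is what was meant. Section 5.3 is headed as concerning therapies and speaks of receiving treatment. Exclusion 7 calls the appendices a list of medications. An exception for treating adverse events fits a drug and not a fruit. Appendix 3 looks like a generic list taken from outside sources, so the food entries may simply have been carried over. This reading is plausible. The presence of St. John's Wort in Appendix 4 shows that these lists go beyond prescription drugs, but a herbal remedy is not a food, so it does not settle the matter. Even so, reading B leaves four entries without a purpose, in a list that site staff are told to consult.

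It can also be said that the harm is inferred. That stands. The pharmacology in Sections 1.5.1 to 1.5.3 describes neither CYP3A4 metabolism of pacritinib nor an inhibitor interaction study, and nothing shows that these foods change exposure.

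Three stronger readings are tempting and are not supported:

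- A reader might take Section 7.6 ("Strong CYP3A4 inhibitors and strong CYP450 inducers, except as needed to treat AEs, with study PI approval") as a second ban on the foods. It does not cite Appendix 3, so it does not bring them in. The conflict rests on 5.3 with Appendix 3 against 5.4.
- A reader might turn time on treatment into patient-years at risk. That would measure only an assumed treatment length. It would not count men who eat these foods, changes in exposure, or events.
- A reader might infer that patients are being told these foods are safe. If the diary or consent form already restricts them, only the protocol wording needs correction.

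**Conclusion.** The inconsistency is in the current text and holds under either reading of the ban: Section 5.4 contradicts Section 5.3, or four entries in Appendix 3 have no function. Its size is four named items of 26. If the foods are covered, the conflict applies from one week before Day 1 until the last dose.

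The clinical effect cannot be sized. The documents give neither the number of men who eat these foods nor any effect on pacritinib exposure. The link to gastrointestinal and cardiovascular events rests on the exposure-safety statement in Section 1.5.5, and on the assumption that the protocol's own listing of these foods as strong inhibitors is meant seriously.

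The point has no bearing on the endpoint, the sample size, the error rates or the primary analysis. It is a safety consistency correction, worth making because it is cheap.

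**What to change.** Replace None in Section 5.4 with:

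*Pacritinib may be taken with or without food. Grapefruit, grapefruit juice, Seville oranges and star fruit (Appendix 3) must be avoided from one week before Day 1 until the last dose.*

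Carry this line into the patient diary and the consent form if it is not already there.

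In exclusion criterion 7, state that the seven-day exclusion applies to the medications in Appendices 3 and 4. Without this, the new sentence in 5.4 would confirm the foods as Appendix 3 items and leave open whether having eaten them in that week makes a man ineligible. Exclusion criterion 8 can stay as it is, because it is limited to systemic treatment.

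Alternatively, if the sponsor judges that no food restriction is needed, delete the four food entries from Appendix 3 and leave Section 5.4 unchanged.

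The first option costs two sentences in 5.4, a clarifying phrase in exclusion 7, and one line in each patient document if absent. The second costs four deletions. Neither adds a visit, a test or a patient.

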5.4 Dietary Restrictions

None.

6 ADVERSE EVENTS: DEFINITIONS, COLLECTION AND REPORTING REQUIREMENTS

6.1 Definitions

6.1.1 Adverse Event

Any untoward medical occurrence in a patient or clinical investigation subject administered a pharmaceutical product and which does not necessarily have to have a causal relationship with this treatment. (International Conference on Harmonisation [ICH], E2A, E6).

This study will utilize the NCI Common Terminology Criteria for Adverse Events (CTCAE) version 5.0, located on the CTEP web site:

https://ctep.cancer.gov/protocolDevelopment/electronic_applications/ctc.htm

AEs may be spontaneously reported by the patient and/or in response to an open question from study personnel or revealed by observation, physical examination, or other diagnostic procedures.

6.1.2 Serious Adverse Event (SAE)

Serious Adverse Event (SAE) means any untoward medical occurrence that results in any of the following outcomes:

- **Death.** Results in death.
- **Life-threatening.** Is life-threatening (refers to an AE in which the patient was at risk of death at the time of the event. It does not refer to an event which hypothetically might have caused death if it were more severe).

- **Hospitalization.** Requires inpatient hospitalization or prolongation of an existing hospitalization.
- **Disability/incapacity.** Results in persistent or significant disability or incapacity. (Disability is defined as a substantial disruption of a person's ability to conduct normal life functions).
- **Pregnancy**
- **Medically important event.** This refers to an AE that may not result in death, be immediately life-threatening, or require hospitalization, but may be considered serious when based on appropriate medical judgment, may jeopardize the patient, require medical or surgical intervention to prevent one of the outcomes listed above, or involves suspected transmission via a medicinal product of an infectious agent. Examples of such medical events include allergic bronchospasm requiring intensive treatment in an emergency room or at home, blood dyscrasias or convulsions that do not result in inpatient hospitalization, or the development of drug dependency or drug abuse; any organism, virus, or infectious particle (e.g., prion protein transmitting Transmissible Spongiform Encephalopathy), pathogenic or nonpathogenic, is considered an infectious agent.

6.1.3 Attribution of an Adverse Event

An assessment of the relationship between the adverse event and the medical intervention, using the following categories:

Definitely Related: *The AE is clearly related to the intervention.* There is clear evidence to suggest a causal relationship, and other possible contributing factors can be ruled out.

Probably Related: *The AE is likely related to the intervention.* There is evidence to suggest a causal relationship, and the influence of other factors is unlikely.

Possibly Related: *The AE may be related to the intervention.* There is some evidence to suggest a causal relationship (e.g., the event occurred within a reasonable time after administration of the trial medication). However, the influence of other factors may have contributed to the event (e.g., the subject's clinical condition, other concomitant events).

Unlikely: *The AE is doubtfully related to the intervention.* A clinical event, including an abnormal laboratory test result, whose temporal relationship to drug administration makes a causal relationship improbable (e.g., the event did not occur within a reasonable time after administration of the trial medication) and in which other drugs or chemicals or underlying disease provides plausible explanations (e.g., the subject's clinical condition, other concomitant treatments).

Unrelated: *The AE is clearly NOT related to the intervention.* The AE is completely independent of study drug administration, and/or evidence exists that the event is definitely related to another etiology.

6.1.4 Expectedness of an Adverse Event

Study Investigator or treating Physician will be responsible for determining whether an AE is expected or unexpected as indicated in the protocol, informed consent form, and/or drug information brochure. An AE will be considered unexpected if the nature, severity, or frequency

of the event is NOT consistent with the risk information previously described for the study intervention.

6.2 Collection and Reporting Requirements for Adverse Events and Serious Adverse Events

6.2.1 Collection of Adverse Events

All (or specify if only certain grade AE needed) adverse events (including SAEs) must be recorded in OnCore® and/or an adverse event log. All AEs required to be collected must be graded according to the CTCAE v5. When possible, signs and symptoms indicating a common underlying pathology should be noted as one comprehensive event. The investigator's or treating physician's assessment of AE attributions must also be documented.

AEs will be collected from the time the subject signs the consent form through 30 days post last dose of study drug(s). AEs will be tracked and followed until resolution, subject withdraws consent, or is lost to follow-up (including subjects who discontinue early). All adverse events collected per the protocol will be followed with appropriate medical management until they are resolved, if they are related to the study treatment, or until the investigator deems the event to be chronic.

Please see section 6.2.2 and table 6 to identify the adverse events that need to be reported.

6.2.2 Reporting of Adverse Events and Serious Adverse Events

Please refer to table 6 below to identify adverse events that meet reporting requirements.

All serious adverse events (SAEs) that occur after the subject has signed the consent form through 30 days post last dose of study drug(s) will be reported. All SAEs will be followed until satisfactory resolution, or until the investigator deems the event to be chronic.

All serious adverse events (SAEs) must also be documented in OnCore®. SAEs (regardless of attribution) will be reported to CTI within 24 hours after the lead investigator learns of the event.

Attribution	SAE				AE		
	Grade 1, 2 & 3		Grade 4 and 5		Grade 3	Grade 4	
	Expected	Unexpected	Expected	Unexpected	Unexpected	Expected	Unexpected

Unrelated Unlikely	IRB ¹ and DSMC ² - Routine Review ³	IRB ¹ and DSMC ² - Routine Review ³	IRB ¹ - Routine Review ³ DSMC ² - Within 5 calendar days	IRB ¹ - Routine Review ³ DSMC ² - Within 5 calendar days	DSMC ² - Routine Review ³	DSMC ² - Within 5 calendar days	DSMC ² - Within 5 calendar days
Possible Probable Definite	IRB ¹ and DSMC ² - Routine Review ³ CTI Biopharma	IRB ¹ and DSMC ² - Within 5 calendar days FDA ⁴ CTI Biopharma	IRB ¹ - Routine Review ³ DSMC ² - Within 5 calendar days CTI Biopharma	IRB ¹ and DSMC ² - Within 5 calendar days FDA ⁴ CTI Biopharma	DSMC ² - Routine Review ³	DSMC ² - Within 5 calendar days	DSMC ² - Within 5 calendar days

Table 6

1. Guidance on adverse event reporting to the IRB is available online at MCW IRB Policies and Procedures.
2. For expedited DSMC reporting, the study coordinator/research nurse must notify the DSMC via email including the subject ID, date of event, grade, relatedness, expectedness, and a short narrative. The DSMC will review data entered into OnCore®.
3. For routine reporting, the events will be reported to IRB as part of the annual continuing progress report and the DSMC will review data entered into OnCore® at the time of scheduled monitoring.
4. Fatal or life-threatening SAEs meeting the criteria indicated in the above table will be reported to FDA no later than seven calendar days after study staff's initial awareness of the event. If the SAE is not fatal or life-threatening and meets the above criteria, the timeline for submitting an IND safety report to FDA is no later than 15 calendar days after study staff's initial awareness of the event. See section 6.2.3 for detailed reporting instructions.

